Furthermore, to date only one study looked into the long-term impact of RMHAs on behavioural attention tests in children with APD. Specifically, sustained auditory and sustained visual attention was examined in 28 children with APD after a 5-month RMHA intervention, without showing any significant change over the intervention period (12). One other study used the Children's Auditory Performance Scale questionnaire, completed by parents at baseline and after 6 months of using the directional microphone hearing aids at school (14). While the Auditory Attention Span subscale of the questionnaire showed significantly improved scores post-intervention, it still remained below what was considered normal cut-off. Parents observed their children at home, when hearing aids were not used, suggesting that the improvement in the subscale scores may have been due to lasting effects on their attentive behaviours. The findings from these two studies are conflicting, but none of the trials used a randomised control design (14).

Aim and hypotheses

In the present study we aim to test the impact of long-term RMHA use on self-reported listening, behavioural SiN performance and to assess behaviourally whether listening-in-spatialised-noise skills change after prolonged RMHA use and to assess the impact RMHA use has on attention skills.

Research questions:

The principal research question was to examine the effects of RMHAs on classroom listening, listening in noise performance, and auditory attention in children with APD.

Hypotheses:

- i. Children with APD who use RMHAs will show greater improvements in classroom listening, listening in noise and sustained auditory attention (unaided) after 6 months of RMHA use in comparison to the APD control group.

¹ The North Western University word-list was used in combination with speech-shaped noise coming from 180° that was individually adjusted (14).

² Words from the Lexical Neighbourhood Test were presented from the front, while a 100-talker babble recording was presented left, right, and behind the subject (12).

- ii. Children with APD who use the RMHA will not show greater improvements in listening in spatialised speech noise and divided and visual attention measures after 6 months of RMHA use in comparison to the APD control group.

Summary of main issues

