We will recruit 26 children, 7-12 years old. All children will have been diagnosed and referred from the Auditory Processing Disorders Clinic at Great Ormond Street Hospital. The total sample size is decided using this power sample: $N = 24$ (total sample size) calculated using the F test for repeated measures between-within interaction Analysis of Variance (ANOVA) based on an estimated 0.5 effect size $f(U)$, 80% power, at 5% significance, using 2 groups and 3 measurement points. To account for a 10% loss due to follow-up, the total sample size of this study was 26 children, aged 7-12.

Inclusion criteria:

1. Diagnosis of APD based on routine clinical tests, administered by qualified audiologists, and requiring the following conditions:

- a) Reported parental SiN and other reported listening difficulties.
 - b) Normal peripheral hearing and middle ear function; i.e. air conduction PTA below 20 dB in all octave frequencies between 250 Hz and 8 KHz (31), middle-ear pressure between -150 to +50 daPa, middle-ear admittance between 0.3 to 1.6 cm³ and ear-canal volumes between 0.4 to 1.0 cm³ (32).
 - c) Abnormal performance on the Auditory Figure Ground (AFG) SiN test of the SCAN-3 C (i.e. at the 1st percentile score as per UK norms), and
 - d) Abnormal performance (-2 SDs from the normative mean) on at least one auditory processing test (i.e. Frequency Pattern Test [FPT], Dichotic Digits Test [DDT], duration pattern test, Gaps-in-Noise [GiN] or random gap detection pattern tests), or a score of -3 SDs from the normative mean on only one auditory processing test (any test from conditions 'c' and 'd'), and/ or abnormal performance (-2 SDs from the mean) on the Spatial Advantage and Total Advantage/ High-cue Speech Reception Threshold (SRT) subtests of the Listening in Spatialised Noise – Sentences (LiSN-S) test.
2. No neurological or pervasive disorder or developmental delay. Children with a diagnosis of Attention Deficit Hyperactivity Disorder, epilepsy, Autism Spectrum Disorder, Developmental Language Disorder, Down Syndrome were excluded from the study.
 3. Non-verbal cognitive ability score (IQ) of 85 or more.
 4. Aged between 7-12 years.
 5. Native English speakers.
 6. No prior use of RMHAs.

Subjects will be semi-randomly assigned to each of two intervention arms. The two groups will be stratified for age and balanced for sex.

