Data were analysed in SPSS 22 statistics software, using a mixed ANOVA, with group as the between-subjects factor with two levels (i.e. control or RMHA) and time the within-subjects factor with three levels (i.e. baseline, 3, and 6 months) .

Other issues:

None of these tests are invasive or unpleasant, and they are conducted in comfortable sound levels (slightly higher than the usual conversational level). Any additional information on the children that might emerge during the study will be reported back to the clinician at the APD clinic to inform the child's management.

All children who participate will receive a book voucher of £10 at the end of each test session. Travel expenses will also be reimbursed (up to £10).

References

3. American Speech-Language-Hearing Association. (Central) Auditory Processing Disorders. Technical Report [Internet]. American Speech-Language-Hearing Association. 2005 [cited 2019 Aug 6]. Available from: <http://www.asha.org/policy/TR2005-00043/>
4. American Academy of Audiology. American Academy of Audiology Clinical Practice Guidelines. Diagnosis, Treatment and Management of Children and Adults with Central Auditory Processing Disorder [Internet]. American Academy of Audiology. 2010 [cited 2019 Aug 6]. p. 1–51. Available from: <http://www.audiology.org/publications-resources/document-library/central-auditory-processing-disorder>

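### Age and sex shape the allocation but are absent from the planned ANOVA; if change over 6 months depends on either, the group-by-time test loses some precision that a pre-specified adjustment would recover cheaply.

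*Combined protocol and SAP*

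**What the plan says.** All references are to the combined protocol and SAP.

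- **Allocation** (Participants and Recruitment, after the inclusion criteria): "Subjects will be semi-randomly assigned to each of two intervention arms", and "The two groups will be stratified for age and balanced for sex". No strata, method or allocation ratio is given.
- **Analysis** (Data analysis): the model is fitted "using a mixed ANOVA, with group as the between-subjects factor with two levels (i.e. control or RMHA"). The only other term it names is the visit, at baseline and at the two follow-up tests. Age and sex are not named as factor or covariate there or anywhere else. The section does not say which effect in the model is decisive.
- **Sample size** (Participants and Recruitment): N = 24 was "calculated using the F test for repeated measures between-within interaction Analysis of Variance (ANOVA"), with an effect size f(U) of 0.5 and "80% power, at 5% significance, using 2 groups and 3 measurement points".
- **First hypothesis** (Hypotheses): children using the devices "will show greater improvements in classroom listening, listening in noise and sustained auditory attention (unaided") than controls.

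The sample size and the first hypothesis together point to group by time as the test of interest.

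**The concern.** Restricting allocation on age and sex removes their contribution to the difference between arms. A model without those terms still counts any variation they cause as error. The test is then calibrated as if a chance imbalance could occur that the design has largely ruled out: its true type I error falls below the nominal level and some power is lost.

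For group by time this needs change over the 6 months to differ by age or sex. That is plausible for age: children spanning 7 to 12 years sit the same tests three times in 6 months and may mature or learn the tests at different rates. At stake is efficiency in a very small trial, together with the freedom to choose covariates after results are seen, since the plan is silent on adjustment. The direction is conservative, so this is not a source of false positive findings.

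**Working it through.** **1. The plan's own figure.** Inputs from the sample size paragraph: f(U) = 0.5, alpha 0.05, 2 groups, 3 visits. With sphericity, λ = f(U)² × (N − 2) × (3 − 1), df1 = 2, df2 = 2(N − 2).

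At N = 24: λ = 0.25 × 22 × 2 = 11 and df = 2, 44, giving power 82.6%. N = 22 gives 78.4% and N = 23 gives 80.6%, so 24 is the smallest N with equal arms that reaches 80%. The stated figure is reproduced.

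**2. Effects on level only.** Group by time is tested on contrasts between a child's own visits. Anything that shifts all three visits equally cancels, so adding age and sex as main effects leaves this F test, and its 82.6% power, unchanged. In a simulation with N = 24, pairs matched on sex and age, within-child correlation 0.5 (assumed), and a strong age/sex effect on level (0.7 SD), null rejection for group by time was 0.054 unadjusted and 0.053 adjusted. The group main effect did become conservative (0.013 against 0.051), but it is not the powered test, and it dilutes any effect with the baseline visit.

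**3. Effects on change.** Assumptions: 24 children, 12:12, allocation stratified for age, a linear age effect on change. R is the share of the variance of linear change that age explains. Within-child error pools a linear and a quadratic contrast. If these have equal variance apart from age, the share of the pooled error explained is R / (2 − R).

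| R (linear change) | Share of pooled within-child error | Null rejection, age omitted |
|---|---|---|
| about 4% | 0.04/1.96 = 2% | about 5% |
| about 15% | 0.15/1.85 = 8% | about 4% |
| about 29% | 0.29/1.71 = 17% | about 3% |

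With age crossed with time in the model, null rejection returns to about 5%.

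**4. Power.** The answer depends on which error f(U) = 0.5 refers to.

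*Reading A: the planned model's own error.* Unadjusted power is 82.6% by construction. Adding age and sex, each crossed with time, takes 2 error df per covariate, so df2 = 44 − 4 = 40, and λ = 11 / (1 − share explained):

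| Share of within-child error explained | λ | Adjusted power |
|---|---|---|
| 0% | 11.00 | 82.3% |
| 5% | 11/0.95 = 11.58 | 84.3% |
| 10% | 11/0.90 = 12.22 | 86.3% |
| 20% | 11/0.80 = 13.75 | 90.2% |

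*Reading B: age variance comes on top of that error.* Over R of about 4-29%, simulated unadjusted power is about 75-81%, against about 82-83% with age in the model.

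**5. Cost if the covariates explain nothing.** 82.6% − 82.3% = 0.3 points, given the balance that the plan promises.

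**The case against.** The strongest case against is that the planned test may lose nothing.

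- **The condition is undocumented.** No association between age or sex and change is given. At around 4% of linear change explained, the effect is negligible. This stands, and it is why no loss can be asserted for this trial.
- **The power target is not breached on the natural reading.** f(U) = 0.5 was set for a model without covariates, so it is most naturally read against that model's error. Planned power then stays above 80%, and adjustment is a gain rather than a repair. This stands; the figures below 80% belong to reading B alone.
- **Sex is less well supported than age.** The graded calculations in step 3 vary age only. Sex belongs in the model because allocation is balanced on it, not because an effect on change has been shown.
- **The allocation is not defined.** The number of strata and the 12:12 split are assumptions, so the exact degree of conservatism cannot be derived.
- **Some scores may already be age-normed.** The inclusion criteria express LiSN-S, also an outcome, against a normative mean. The plan does not say which score form is analysed. Normed scores would gain less.

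A reader might infer that omitting age and sex in itself inflates the error term, pushes the type I error below 5% and leaves the trial underpowered. The documents do not support that: the powered test already removes stable differences between children, and nothing in the plan shows that trajectories differ by age or sex.

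None of this removes the mismatch between allocation and analysis, or the value of settling it in advance.

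**Conclusion.** The mismatch is real and its consequence is conditional. Age and sex are used to form the groups and are missing from the model. For group by time this matters only if change over 6 months depends on age or sex; the test is then somewhat conservative and less precise than it could be. The plausible size runs from nothing to a true type I error of about 3% at the top of the assumed range, with a power gain from adjustment of a few points: up to about 8 at 20% of within-child error explained (90.2 − 82.6 = 7.6).

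These figures rest on assumed associations, equal arms, age-stratified allocation, sphericity and 24 evaluable children. The claims that need none of these assumptions are that the plan is silent on adjustment and that it does not name its decisive test. It is a cheap improvement offering an optional precision gain, not a threat to validity.

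**What to change.** In the Data analysis section, state that the group-by-time interaction is the test of interest. Add age (continuous, mean-centred) and sex as pre-specified covariates for every outcome, each crossed with time, and give the reason: allocation is stratified for age and balanced for sex. Centring keeps the time effect interpretable at the average age rather than at age zero. Crossing with time is essential, because main-effect terms alone leave the interaction test unchanged.

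The cost is a sentence or two and no new data, since both variables are needed for allocation. The interaction test gives up 4 error degrees of freedom (44 to 40). If the covariates explain nothing, power drops by about 0.3 points when the groups are balanced as planned, and by somewhat more if they are not. The gain will be smaller for outcomes analysed as age-normed scores, so the section should also say which score form is used.

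### The planned ANOVA uses the pre-intervention score as an outcome level; using it as a covariate would guard against chance baseline gaps and usually gain some precision at almost no cost

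*Combined protocol and SAP*

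**What the plan says.** The Data analysis section of the combined protocol and SAP is one sentence long. It specifies a mixed ANOVA in which the two arms, RMHA and control, are compared between children. For the visits it makes "time the within-subjects factor with three levels (i.e. baseline, 3, and 6 months". No covariate, planned contrast or other adjustment for the baseline score appears anywhere in the document.

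The sample size under Participants and Recruitment matches that model. It rests on the F test for the interaction of arm and visit, and its inputs are given as "based on an estimated 0.5 effect size $f(U)$, 80% power, at 5% significance, using 2 groups and 3 measurement points". The result was 24 children, raised to 26 for dropout.

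The same section describes allocation to the two arms as semi-random, stratified for age and balanced for sex. Nothing balances the arms on the baseline value of an outcome. Research Design and Methodology places the baseline tests before the intervention starts, and the hypotheses concern greater improvement than control after 6 months.

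**The concern.** A score taken before the device is used cannot carry a device effect. Under random allocation, any difference between arms in that score is chance. When baseline is a level of the time factor, contrasts of 3 or 6 months against baseline subtract the whole of that chance difference, although only a fraction rho of it is expected to persist at follow-up. The omnibus group-by-time test contains these contrasts.

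With 12 or 13 children per arm, sizeable chance gaps are common. At stake are the trustworthiness of the estimate in the one trial actually run, and precision that the data already collected could supply.

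**Working it through.** **Inputs from the document.** Two groups, three visits, f(U) = 0.5, 5% significance, 80% power, N = 24 before dropout (Participants and Recruitment); the three-level model (Data analysis).

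**Assumptions.** Equal SDs at each visit, the same correlation rho between any two visits, and 1:1 allocation. The document gives neither rho nor the allocation ratio, so a range of rho is shown.

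**1. The plan's own figure.** With k = 2 groups and m = 3 visits, the noncentrality is f(U)² × (N - k) × (m - 1) = 0.25 × 22 × 2 = 11, on 2 and 44 degrees of freedom with sphericity. Power is 82.6% at N = 24 and 78.4% at N = 22. The smallest even N reaching 80% is 24, so the stated figure reproduces. The sample size and the planned test are consistent.

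**2. Size of chance gaps.** The SD of the baseline mean difference is √(2/n) outcome SDs: 0.408 at n = 12 per arm and 0.392 at n = 13. The probability of a gap above 0.5 SD in either direction is 22% and 20%.

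**3. Effect of a gap g on the estimate.** Given g, the expected follow-up difference is (effect + rho × g). Change subtracts g and leaves (effect - (1 - rho) × g). For g = 0.5 SD the shift is 0.25 SD at rho 0.5, 0.15 at 0.7, 0.10 at 0.8 and 0.05 at 0.9. In simulation (20,000 trials per setting, 12 per arm) the 6-month change estimate correlated with the baseline gap at -0.50, -0.39, -0.31 and -0.22 at these values of rho. The baseline-adjusted estimate correlated at about zero. The planned interaction test held a type I error of about 5%.

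**4. Precision at 6 months.** The variance of the arm difference is proportional to 2(1 - rho) for change and to (1 - rho²) for ANCOVA, a ratio of (1 + rho)/2. Estimating the slope costs a factor of about 1 + 1/(24 - 4) = 1.05. The equivalent N is 24 divided by the resulting ratio.

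**5. Power at 6 months.** Take an effect d that is equal at 3 and 6 months. With 12 per arm the interaction noncentrality is 4d²/(1 - rho). Setting it to 11 gives d = √(11(1 - rho)/4). The 6-month change test then has t noncentrality d/√(2(1 - rho) × 2/12) = √8.25 = 2.87 on 22 df, which is 78.4% power for every rho. For ANCOVA, divide 2.87 by the square root of the ratio with slope cost and use 21 df.

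| rho | d (SD) | (1 + rho)/2 | with slope cost | equivalent N | change power | ANCOVA power |
|---|---|---|---|---|---|---|
| 0.5 | 1.173 | 0.75 | 0.79 | 30.5 | 78% | 87% |
| 0.7 | 0.908 | 0.85 | 0.89 | 26.9 | 78% | 83% |
| 0.8 | 0.742 | 0.90 | 0.95 | 25.4 | 78% | 80% |
| 0.9 | 0.524 | 0.95 | 1.00 | 24.1 | 78% | 78% |

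**6. The two-df joint test.** The plan's own test is the omnibus interaction, so it was also compared with a two-df joint test of the baseline-adjusted group differences at 3 and 6 months (8,000 simulated trials, N = 24).

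| rho | effect | planned interaction | baseline-adjusted |
|---|---|---|---|
| 0.5 | constant | 82.8% | 91.2% |
| 0.7 | constant | 82.1% | 85.1% |
| 0.7 | growing linearly | 83.5% | 84.5% |
| 0.8 | growing linearly | 82.1% | 81.4% |

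**The case against.** The strongest reply is that this is a choice between two valid analyses. The planned test keeps its error rate, is unbiased on average, and is the test the trial was sized for. The gain depends on an unknown rho, and on the two-df test it is 1 to 3 points at rho 0.7 and slightly negative in one setting at rho 0.8. The 78% baseline for the 6-month comparison belongs to a change test that the plan does not name. All of that stands. It limits the point to an efficiency gain plus protection against the imbalance that happens to occur; it does not remove either.

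Allocation is described only as semi-random. If it is not properly random, neither analysis is automatically unbiased. If it is, age stratification would reduce gaps on any age-related raw score, so the 20-22% is a figure for simple randomisation. The Data analysis section is also in the past tense, so replacing the main model may be a post hoc change.

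Three stronger readings are tempting and not supported:

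- **That the planned analysis is biased or wrong.** The shift is conditional on the observed gap and averages to zero under randomisation.
- **That the point holds for any time contrast.** Comparing 3 with 6 months does not involve baseline.
- **That it is worse for LiSN-S because of regression to the mean.** Some children may qualify through "abnormal performance (-2 SDs from the mean) on the Spatial Advantage and Total Advantage/ High-cue Speech Reception Threshold (SRT) subtests". But eligibility rests on routine clinical tests given by audiologists, while LiSN-S is listed separately among the study assessments and given by the PhD student. The document does not show that the qualifying score is the analysed baseline. A simulation with no device effect, reliability 0.7 and an uneven split of such children (9 of 12 against 3 of 12), all assumed, gave a bias of 0.00 SD for change and -0.18 SD for ANCOVA with a separate study baseline. Change was biased (0.28 SD) only when the qualifying score itself served as baseline.

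**Conclusion.** The point holds as a cheap improvement. The plan enters the baseline score as an outcome level, nothing in design or analysis balances or adjusts for it, and a gap above 0.5 SD would arise in roughly one trial in five. Such a gap would move the change estimate by 0.05 to 0.25 SD over rho 0.9 to 0.5. The gain in 6-month precision is worth about six children at rho 0.5, about three at 0.7, about one at 0.8 and none at 0.9. These sizes rest on equal SDs, equal visit correlations, 1:1 random allocation and an effect that is constant over the two follow-ups. The sample size calculation is not in error on this account.

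**What to change.** In the Data analysis section, make the 3- and 6-month scores the outcomes (time with two levels). Enter the child's own study-baseline score on that outcome as a covariate, together with its interaction with time, and report the baseline-adjusted group difference at 6 months. Apply this to every outcome. Keep the three-level ANOVA as a sensitivity analysis. If the data have already been analysed, report the baseline-adjusted model alongside the planned ANOVA and label it as added later.

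The cost is wording and one degree of freedom per covariate. No new data or visits are needed, and SPSS 22 can fit the model. The downside is that nothing is gained in precision if visits correlate near 0.9, and a two-df joint test can lose a fraction of a point of power when correlation is high and the effect grows linearly.
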